### 3.0. METHODOLOGY

### 3.1. Registry Design

The Russian Severe Asthma Registry is a prospective multicenter, non-interventional observational study for patients with severe bronchial asthma (SA).

All patients included in the RSAR platform will be periodically observed during routine visits to the hospital with a follow-up of up to five years.

In the RSAR conductance there is no provision for any intervention in routine clinical practice, including the use of the study therapy / treatment methods or special research methods. From the day the project begins, the physician will collect data on all patients with SA who have visit as outpatient or hospitalized patient and who meet the inclusion criteria for in this study.

The study includes a retrospective part - an analysis of the medical records of patients available at the time of their inclusion in the study.

Patients with a confirmed diagnosis of SA (according to inclusion criteria) will be included in the study sequentially and observed for 5 years.

The period of patient's inclusion - from 03.2018 till 11.2022.

The observation period is from 03.2018 till 11.2022.

The approximate period of the Registry work is from 03.2018 to 12.2022.

The target sample size is up to 7,000 patients with SA over a period of 5 years.

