The registry improved the detection of IPF: currently there are 519 patients in, while there are total number of about 1000 IPF patients according to epidemiology in the Russian Federation. About 35% of patients in the IPF Registry are of working age. The functioning of the IPF Registry led to an improvement in the quality of medical care for patients with IPF. Within the framework of IPF Registry, 236 online consultations / opinions of federal or regional experts were conducted. During the work of the IPF Registry, the number of patients receiving specific antifibrotic therapy, which is the treatment of choice, has increased according to current recommendations: 97% of patients (59 of 61) receive nintedanib, registered in Russia with indication IPF. The IPF Registry is of high scientific and practical value and of great social significance for the diagnosis and treatment of this life-threatening disease.

The development of the Russian Severe Asthma Registry (RSAR) with a planned number of patients (CRFs) of 7,000 involving researchers from more than 30 cities has the potential to become an important Russian platform to research and a get a better understanding of the heterogeneity of the BA. the same as the rationale for proper use and monitoring the impact of BA treatment with new drugs.

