### 3.2. Draft Cities Initiation

The participation of cities and recruitment of patients in the RSAR is expected:

Period, years	Number of participating cities (health facilities)	Number of SA patients CRFs
03.2018-12.2018	30 (100 health facilities)	2000
01.2019-12.2019	30 (100 health facilities))	2000
01.2020-12.2020	30 (100 health facilities))	1000
01.2021-12.2021	30 (100 health facilities)	1000

01.2022-11.2022	30 (100 health facilities))	1000
-----------------	-----------------------------	------

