### **3.7. Registry Follow-up**

Since the study is in the form of a Registry - non-interventional observational study - there is no planned intervention in the common clinical practice of patient management, the number of follow-up visits will be based on existing recommendations and protocols for managing patients with asthma in the Russian Federation and the patient's needs. It is assumed that the patient will visit health facilities once in 3 months. The frequency of visits depends on the initial level of control of asthma in the patient, the response to treatment.

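### No patient can be observed for the 5 years stated in 3.1, and 4.5 does not define the denominator of the year 1–4 percentages for patients enrolled too late to reach them

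*Combined protocol and SAP*

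**What the plan says.** Section 3.1 describes follow-up in two ways. One sentence says that patients "will be included in the study sequentially and observed for 5 years". Another says that they are "periodically observed during routine visits to the hospital with a follow-up of up to five years". The same section gives identical dates for the two processes: "inclusion - from 03.2018 till 11.2022" and "The observation period is from 03.2018 till 11.2022". It then adds: "The approximate period of the Registry work is from 03.2018 to 12.2022". The Milestones table agrees, with data entry ending in 11/2022 and the last analytic report in 12/2022.

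Section 1.2 describes the registry "with a planned number of patients (CRFs) of 7,000". The table in 3.2, introduced by "The participation of cities and recruitment of patients in the RSAR is expected", plans 2,000, 2,000, 1,000, 1,000 and 1,000 CRFs for 2018 to 2022, so recruitment runs to the last month of observation.

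Section 2.2 sets secondary objectives at years 1, 2, 3 and 4 for the whole sample and, where appropriate, for subgroups. No visit window is attached to them. Visits are routine; 3.7 says only: "It is assumed that the patient will visit health facilities once in 3 months".

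Section 4.5 takes everyone in the analysed population as the denominator for percentages, whether or not the value is missing, and adds a *Missing* row when needed. The only exception is for nested questions. Section 4.4 allows dropouts' data to be used as far as their completed visits permit, and restricts the endpoint analysis to patients diagnosed within 6 months of inclusion.

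**The concern.** The fixed 5-year statement cannot be met under the plan's own dates. With staggered entry and a common close, potential follow-up depends on enrolment date, and most of the planned sample enters too late for year 4.

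This matters because 4.5 has one general denominator rule and does not say who belongs to the analysed population at year k. Combining the whole-sample wording of 2.2 with the rule in 4.5 would count patients not yet due in the denominator and put them in the *Missing* row. The year-k percentages (exacerbation categories, ACQ-6 uncontrolled, maintenance therapy, OCS, emergency calls, disability sheets) would then fall year by year because of recruitment timing alone. The *Missing* row would mix patients never due with data truly lost. Two analysts following the plan could report quite different year-4 percentages from the same data.

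**Working it through.** **Inputs.** Window and dates from 3.1; yearly CRFs from 3.2; objectives at years 1–4 from 2.2. Assumption: one CRF is one new patient, which 1.2 and the 7,000-patient goal in 3.4 support. All counts are before dropout and before the newly-identified restriction in 4.4.

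**Planned total.** 2,000 + 2,000 + 1,000 + 1,000 + 1,000 = 7,000, which reproduces the stated target.

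**Window.** 10 + 12 + 12 + 12 + 11 = 57 months to the end of 11.2022, or 58 to the end of 12.2022. Five years is 60 months, so 0 of 7,000 can reach it.

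**Lower bound at 48 months.** Even with a close on 31 December 2022, a full 48 months requires enrolment in 2018. At most 2,000 qualify, so at least 5,000/7,000 = 71.4% do not. This needs no assumption about accrual within 2018.

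**Numbers that can reach exactly year k.** Close on 30 November 2022, even accrual within each row of 3.2 (the 2018 row covers 10 months):

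| Year k | Calculation | N_k | Cannot reach | 7,000/N_k |
|---|---|---|---|---|
| 1 | 5,000 + 1,000 × 11/12 | 5,917 | 15.5% | 1.2 |
| 2 | 4,000 + 1,000 × 11/12 | 4,917 | 29.8% | 1.4 |
| 3 | 2,000 + 2,000 × 11/12 | 3,833 | 45.2% | 1.8 |
| 4 | 2,000 × 9/10 | 1,800 | 74.3% | 3.9 |

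**Sensitivity at year 4.**
- Close on 31 December 2022: 2,000 reach 48 months; 71.4% cannot.
- Visits from month 45 accepted (assumed window, 30 November close): 2,000 + 2,000 × 2/12 = 2,333; 66.7% cannot. The 71.4% bound belongs to a full 48 months. With this window the bound free of accrual assumptions drops to 3,000/7,000 = 42.9%, reached only if the whole 2019 intake enrols by the end of February.

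**Effect on a percentage if all 7,000 form the denominator.** Reported value = true value × N_k/7,000, taking all due patients as observed. With an assumed constant 40%, years 1–4 would show 33.8, 28.1, 21.9 and 10.3%. At year 4, assumed true values of 20% and 50% would show as 20 × 1,800/7,000 = 5.1% and 50 × 1,800/7,000 = 12.9%. The shrinkage factor at year 4 is 3.9 for exactly 48 months with even accrual, 3.5 in the most favourable case (2,000 patients) and 3.0 with the month-45 window.

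**The case against.** The strongest reply is that the 5 years is loose wording. Section 3.1 also uses a 5-year period for the project as a whole, and its 'up to' wording suits staggered entry to a fixed close, which is ordinary in a registry. That stands as an explanation, but the fixed statement is still there and is unattainable.

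A second reply is that an analyst would naturally use only patients who reached year k. Someone enrolled in 2022 has no year 4, and the dropout provision in 4.4 hints at period-specific populations. Counts and a *Missing* row are displayed, so a reader could recompute percentages among non-missing patients. This is fair, but the plan does not state that choice, the literal text of 2.2 with 4.5 points the other way, and the counts alone would not separate not-due from truly missing.

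Several stronger readings are tempting, and the documents do not support them:

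- *Section 4.5 sets no denominator.* It sets a general one; what is absent is its definition by follow-up year.
- *Year-4 results will be diluted about fourfold.* That follows only if all 7,000 are used, and the percentages shown above rest on assumed true values.
- *The field statuses in 4.4 are deficient because none covers patients not yet due.* They code blank fields in a form. Due status can be derived from visit dates and the close.
- *The comparison of leavers with completers is invalid.* Section 4.4 refers to leaving the register before its completion; 4.8 refers to leaving ahead of schedule and requires a documented cause. Together these largely separate dropout from administrative end. Matching leavers on potential follow-up would be a refinement.

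**Conclusion.** The point holds, and should be fixed. No patient can be observed for 5 years; the maximum is about 57 months. Provided that each CRF is a new patient, at least 71.4% of the planned 7,000 cannot complete a full 48 months. With even accrual and a 30 November 2022 close it is about 74%, or about 67% if month 45 counts. About 5,900, 4,900, 3,800 and 1,800 patients can reach exactly years 1 to 4, and the newly-identified restriction may reduce the numbers analysed. If CRFs are not all new patients, these figures change, but the impossible 5 years and the undefined year-k population remain.

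A reader might infer that the registry's main result is compromised. It is not: the primary objective is measured at enrolment, and year-k means among observed patients are not diluted. The consequence is confined to the year 1–4 percentages and their *Missing* rows.

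**What to change.** - **3.1:** reconcile the follow-up wording with the dates, for example: observed from enrolment to the end of observation in 11.2022, at most about 57 months.
- **4.5:** state a visit window for each yearly assessment. Set the denominator of each year-k percentage to patients whose enrolment date allows that assessment, including its window, before the end of observation. Count *Missing* only among them and show those not yet due on a separate line.
- **4.5:** give the expected N for each year with the accrual assumption, and say that it is before dropout and before the restriction in 4.4.
- **4.4 and 4.8:** one sentence saying that administrative end of observation is not dropout is enough.

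The cost is a wording change to the protocol and SAP, with no added patients or visits. The downside is that the stated follow-up and the late-year numbers will look less favourable.

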### 3.2. Draft Cities Initiation

The participation of cities and recruitment of patients in the RSAR is expected:

Period, years	Number of participating cities (health facilities)	Number of SA patients CRFs
03.2018-12.2018	30 (100 health facilities)	2000
01.2019-12.2019	30 (100 health facilities))	2000
01.2020-12.2020	30 (100 health facilities))	1000
01.2021-12.2021	30 (100 health facilities)	1000

01.2022-11.2022	30 (100 health facilities))	1000
-----------------	-----------------------------	------

### 3.3 Data Collection

The main data source within the RSAR will be an electronic database of patients developed on the basis of the "Medical online platform ROSMED.INFO", which is the own development of LLC "RSMI".

The attending physicians of patients with SA will enter information online in the electronic database. As investigation centers will be used health facilities of federal and regional levels, which include specialized pulmonological and allergic departments. These centers have the opportunity to include the largest number of patients with SA in the study, and they also have extensive experience in the management and monitoring of such patients. The total number of health facilities is 100. The centers participating in the study will collect data on all patients diagnosed with SA who have signed written informed consent to participate in the study. Data collection will be carried out on a regular basis during routine patient visits to a doctor or in case of hospitalization. In the work period of this project, no special additional procedures for collecting information will be used. The information will be collected from outpatient cards and / or case histories, based on data received by the physician during routine examination of the patient. Visitors of [www.rosmed.info](http://www.rosmed.info) site can not participate in the RSAR study without first being invited by the attending physician.

### 3.4. Patient Population

Patients receiving step 4 and 5 treatment (according to GINA, 2017) in accordance with the uncontrolled asthma severity (J.45) in health facilities in accordance with local regulatory / ethical requirements. The goal is to include up to 7,000 patients in RSAR throughout Russia during the entire study period.

Signed informed consent will be collected from patients in order to use data in accordance with RF legislation, and to gain approval of the RSAR study by the Independent Interdisciplinary Ethical Review Committee of the Clinical Studies (Committee) - (<http://ethicuni.ru>).

The role of the Committee is to verify and approve the scientific significance of research objectives. The purpose of the Committee is to ensure that the research database is clinically appropriate and continues to bring real benefits to patients, public health and health organization system.

The study will collect the following data on patients with SA:

- Personal data.
- Patient demographics.

- Anamnesis of the disease, including previous exacerbations, allergic status and current status monitoring.
- Concomitant diseases, including atopic dermatitis, allergic and non-allergic rhinitis, chronic rhinosinusitis with or without polyps.
- Medications prescribed for the treatment of asthma, including data on patient adherence to prescribed treatment, where applicable and assessment of the inhalation technique.
- Treatment outcomes, including asthma control status (control of GINA 2017), quality of life and professional history.
- Spirometry data.
- Biomarkers (blood eosinophils, sputum eosinophils, IgE, and FeNO, where possible).
- Patient's basic therapy, including use of OCS and biological agents.
- The economic burden of asthma in patients (disability sheets, ambulance calls, etc.).
- Evaluation of the frequency and severity of BA exacerbations.

The data including these estimates will be entered into the electronic database of RSAR for storage and subsequent impersonal analytics. Data from any existing registries of patients with severe asthma may also be entered.

For compatibility, the existing data will be sorted in accordance with the standard data collection fields / codes established by the RSAR monitoring group.

### 3.5. Inclusion Criteria

- Patients aged 12 years or older.  
Patients with confirmed diagnosis of severe asthma.
- Patients receiving treatment according to GINA step 5 or uncontrolled for 4 step. Uncontrolled patients are defined as having symptoms of severe asthma or frequent exacerbations.  
Signed informed consent.

---

 Severe symptoms of BA (Guideline of European Respiratory Society (ERS)/American Thoracic Society (ATS)) (2):

(a) BA with uncontrolled symptoms; ACT < 20, ACQ > 1,5;

(b) Limited air-flow rate, for example: FEV1 < 80 % of the norm (along with FEV1/FES at the lower limit of the norm or less) after wash-out period from the bronchodilators;

(c) Severe exacerbation and hospitalization, being in the ICU or on the mechanical ventilation of lungs over the past year.

 Frequent severe exacerbations of BA (guidelines ERS/ATS) (2):

Frequent severe exacerbations of BA (2 or more courses of systemic glucocorticoids over the past year).

### **3.6. Exclusion Criteria**

- Intermittent, mild, moderate BA, before verification of the diagnosis.
- COPD.
- Diseases of the respiratory system, such as tuberculosis, sarcoidosis, IPF, lung cancer.
- Vasculitis, systemic connective tissue diseases.
- Neoplasm.
- Written refusal of the patient to participate in the study after signing an informed consent.

### **3.7. Registry Follow-up**

Since the study is in the form of a Registry - non-interventional observational study - there is no planned intervention in the common clinical practice of patient management, the number of follow-up visits will be based on existing recommendations and protocols for managing patients with asthma in the Russian Federation and the patient's needs. It is assumed that the patient will visit health facilities once in 3 months. The frequency of visits depends on the initial level of control of asthma in the patient, the response to treatment.

### **3.8. Consent Procedures**

Participants will be provided with full information about the planned study, their rights and opportunities, after which it will be offered to sign the informed consent, which is a prerequisite for the patient's participation in the Registry.

## **4.0. DATABASE**

### **4.1. Data Acquisition**

With each physician-investigator a civil law agreement will be concluded that regulates the work of the physician within the framework of the project. A cooperation agreement will be concluded between the project technical executor, LLC RSMI, and the supervising organization of the IPO RRS, which will ensure the right of IPO RRS to legally own the accumulated database on patients with severe asthma.

### **4.2. Data Management**

Data from patients with SA will be entered into the electronic CRF by physicians-investigators within a limited time after receiving the diagnostic / consultation results. The CRF is an integrated part of the Universal Medical Complex of Medical Organization and Informatization for the collection, dynamic clinical and epidemiological surveillance and analysis of data in the

remote access mode "ROSMED.INFO", quality control and reliability of the information entered will be checked online by the project manager of LLC "RSMI" within the framework of existing SOPs and quality management standards.

The data of SA patients CRFs will be stored electronically in a secure database, with an obligatory database backup procedure, as well as with a preliminary assessment of the security threats for their elimination (RSMI regulatory document - "Security Threat Model").

Backup information is stored on the servers (databases, data catalogs on file servers, general catalogs of departments and departments).

In parallel, the data will be copied on paper carriers, their storage will be carried out in water and fireproof safes.

Instructions for the operation of the data manager of the RSAR include the full procedure for working with personal data and are available for audit.

A separate data management plan describes all the functions, processes and specifications for data collection, retrieval, sending, cleaning and validation. Electronic CRFs will include a programmed version for instant feedback, if data are not available, go beyond acceptable limits, are illogical and potentially erroneous. This minimizes general data entry errors. A collaborative manual data validation process will be conducted based on plan parameters. In the electronic research data recording system (EDS), special requests will be generated, requiring further explanations.

High data quality standards will be maintained, the processes and procedures used systematically will ensure the highest possible accuracy of the data submitted for analysis. The data quality will be improved through a series of programmed checks to automatically detect abnormal data or data beyond the specified limits. All data modifications will be registered in the audit log.

### **4.3. Registry Coding**

The project work group consisting of representatives of the supervising organization and technical specialists of RSMI LLC will agree on a standardized set of basic and long-term indicators, and will hold regular meetings to ensure long-term expert input through the development, expansion of the register and the achievement of research objectives.

The technical executor of the project, LLC RSMI, should provide the opportunity, if necessary, to convert the accumulated database into a format that corresponds to the standardized clinical codes and terms contained in the dictionary of the systematized nomenclature of medical clinical terms (SNOMED CT), which allows to recognize the clinical sequence of ICD and read the encoding, which will be able to present the data at the detailed level required for the purpose of coding the register. SNOMED CT was developed by the International Health Terminology Organization (IHTSDO), and is currently available in English and Spanish versions.

#### **4.4. Statistics analysis**

Primary and secondary statistical indicators will be presented using descriptive statistics methods. Qualitative variables will be presented in the form of incidence and percentage. The quantitative variables will be represented by numerical values, standard deviation indicators, minima and maxima, median and interquartile range. The frequency and severity of adverse events / reactions will be documented according to the Medical Dictionary of Regulatory Terminology, version 16.1. When analyzing the outcome of the disease among patients on therapy (drug), statistical analysis will be performed in a subgroup of newly identified patients. Evaluation of the outcome of SA can be determined by achieving a sufficient number of patients in a subgroup of newly identified patients and patients undergoing therapy (SA). The lack of comparison between groups of patients is due to the inaccuracy of these therapies in the history and treatment approaches.

In the course of the analysis, the standard statistical characteristics of morbidity, prevalence of the disease (SA) and their dependence on the basic demographic indicators (sex, age) will be assessed. The statistical analysis of the endpoints will be performed for patients with a diagnosis period of no more than 6 months from the date of inclusion in the register (a subgroup of newly identified patients) and also when the required amount of statistical data is collected within the register database.

The analysis will use standard methods of descriptive, frequency, logistic statistical analysis.

Hypotheses of the study. The main goal of the study is to obtain statistical estimates of the target epidemiological characteristics, formally asking questions about hypotheses of the study in this case is not applicable. After receiving the estimates, they are expected to be compared with similar ones, known in the foreign and domestic literature and official statistics.

Within the Registry, measures should be taken to collect data on the maximum number of patients within the claimed sample. In the absence of information within the fields of the individual registration card, the validating authority should separate information on the statuses "negative value", "no data", "not investigated".

The data of patients dropped out of the register during the observation will be analyzed and used to calculate the primary points, if the number of completed visits allows, the data can be used to analyze part of the parameters of the observation period. The initial characteristics of patients dropped out of the register before its completion will be compared with the characteristics of patients with a fully completed observation period, taking into account the proportionality of the data (the number of "dropped out" patients).

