73	Allergic tests (determination of specific IgE in blood)	- Was specific IgE in blood positive for seasonal allergens?	No/Yes
74	Allergic tests (determination of specific IgE in blood)	+ Indicate the seasonal allergens to which specific IgE in blood was positive (select all applicable)	Trees pollen Weeds pollen Grasses pollen
75	Allergic tests (Scarification test (ST))	-ST date	DD / MM / YYYY
76	Allergic tests (Scarification test (ST))	- Was the ST positive for year-round allergens?	No/Yes

77	Allergic tests (Scarification test (ST))	Indicate year-round allergens (for ST) (select all applicable)	Dust mite (eg D. Pteronyssinus) / cat's hair / mixture of molds / dog hair / aspergillus / other (please specify)
78	Allergic tests (Scarification test (ST))	- Was the ST positive for seasonal allergens?	No/Yes
79	Allergic tests (Scarification test (ST))	+ Indicate the seasonal allergens to which the ST was positive (select all applicable)	Trees pollen Weeds pollen Grasses pollen
80	Asthma symptom control	Do patients experience symptoms during the day? (more than twice a week)	No/Yes
81	Asthma symptom control	Does the patient have any limitation of physical activity due to asthma? For what period of time?	No/Yes
82	Asthma symptom control	Does patient awake For what period of time?	No/Yes
83	Asthma symptom control	Does patient need to use asthma symptom relief drugs more than 2 a week?	No/Yes
84	Asthma symptom control	Is the patient's lung function (PEF or FEV1) < 80% of prognosed or best per sonal result (if known)?	No/Yes
85	Drugs to manage asthma	Does patient use currently oral GCS?	No/Yes – Dose - Duration of use - Registered adverse

			effects of OCS
86	Drugs to manage asthma	Did patient use OCS earlier?	No/Yes – Dose - Duration of use - Registered adverse effects of OCS
87	Drugs to manage asthma	-Date of OCS use start	DD / MM / YYYY
88	Drugs to manage asthma	Does patient use currently combined therapy (ICS+LABA)? (please, select from the list)	No budesonide + formoterol fluticasone furoate + vilanterol fluticasone propionate + salmeterol beclomethasone + formoterol other
89	Drugs to manage asthma	Does the patient currently take ICS + LABA as a fixed or free combination?	- Fixed combination - Free combination
90	Drugs to manage asthma	- Date of onset of combined ICS+LABA therapy	DD / MM / YYYY

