91	Drugs to manage asthma	Is the patient currently taking ICS (only)? (please select from the list)	No triamcinolone acetonide mometasone furoate fluticasone propionate fluticasone furoate ciclesonide flunysonide budesonide beclomethasone other
92	Drugs to manage asthma	- Date of start / end of ICS intake	DD / MM / YYYY
93	Drugs to manage asthma	Is the patient currently taking LABA (only)? (please select from the list)	No formoterol salmeterol indacaterol olodaterol other
94	Drugs to manage asthma	- Date of start / end of LABA intake	DD / MM / YYYY
95	Drugs to manage asthma	Is the patient currently taking LAMA (only)? (please select from the list)	No aclidinium tiotropium umeclidinium glycopyrronium

			other
96	Drugs to manage asthma	- Date of start / end of LAMA intake	DD / MM / YYYY
97	Inhalation technique assessment.	Appropriate Inappropriate (if so, the next question) Crucial mistakes Present Absent	
98	Drugs to manage asthma	Is the patient currently taking theophylline? (please select from the list)	No theophylline aminophylline other
99	Drugs to manage asthma	- Date of start / end of theophylline intake	DD / MM / YYYY
100	Drugs to manage asthma	Is the patient currently receiving a leukotriene receptor antagonist (LTRA)? (please select from the list)	No zafirlukast montelukast other
101	Drugs to manage asthma	- Date of start / end of LTRA intake	DD / MM / YYYY
102	Drugs to manage	Is the patient currently receiving treatment targeted on	No/Yes

	asthma	immunoglobulin E (Anti-IgE)? (omalizumab is prescribed)	
103	Drugs to manage asthma	Date of start / end of Anti-IgE intake?	DD / MM / YYYY
104	Drugs to manage asthma	Is the patient currently receiving treatment targeted on IL-5 (Anti-IL-5)? (please select from the list)	No reslisumab mepolizumab benalizumab dupilumab (?) tezepelumab (?) other (new biotechnological preparations will be added after approval and start of use in Russia)
105	Drugs to manage asthma	Date of start / end of Anti-IL5 intake?	DD / MM / YYYY
106	Drugs to manage asthma	Does the patient currently receive antibiotic treatment with the macrolide group? (please select from the list)	No azithromycin clarithromycin erythromycin roxithromycin fidaxomycin telithromycin other
107	Drugs to manage	Date of start / end of macrolide	DD / MM / YYYY

	asthma	intake?	
108	Compliance	Is there a non-compliance with the treatment regimen?	No Yes: - dosage; - frequency of reception; - absence of all prescribed medications; - other

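### Outcome on a drug is analysed in a subset defined by time since diagnosis, not time since drug start, so it can mix established users with starters and, as written, omits longer-diagnosed starters

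*Combined protocol and SAP*

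**What the plan says.** Section 4.4 (Statistics analysis) of the combined protocol and SAP sets the population for outcome on treatment: "When analyzing the outcome of the disease among patients on therapy (drug), statistical analysis will be performed in a subgroup of newly identified patients". It describes the subgroup as "patients with a diagnosis period of no more than 6 months from the date of inclusion in the register". No new-user or washout rule appears anywhere in the document.

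Two other clauses in section 4.4 bear on the population. One makes evaluation of outcome depend on "achieving a sufficient number of patients in a subgroup of newly identified patients and patients undergoing therapy (SA". The other follows the six-month definition and adds "and also when the required amount of statistical data is collected within the register database". Neither gives a number or a defined set of patients.

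On entry, section 3.5 requires "Patients receiving treatment according to GINA step 5 or uncontrolled for 4 step". Section 3.1 says that "the physician will collect data on all patients with SA who have visit as outpatient or hospitalized patient", subject to the inclusion criteria and with no limit on disease duration.

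The Appendix (section 9) collects treatment dates, among them "Date of start / end of Anti-IgE intake" (item 103) and "Date of onset of combined ICS+LABA therapy" (item 90). Item 87 dates the start of oral corticosteroids (OCS) and item 105 covers anti-IL-5 treatment. Section 2.0 lists evaluation of the efficacy and safety of pharmacotherapy among the registry's aims.

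**The concern.** A description of what happens on a drug needs a time zero tied to that drug. Time since diagnosis does not supply one. Of two patients in the subset, one may have been on the drug since before inclusion and the other may begin it well into follow-up. Established users are those who have stayed on the drug; people who stopped early are under-represented among them. Pooling them with starters gives a figure that describes neither group.

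Someone diagnosed more than six months before inclusion who begins a biologic on the registry is outside the subset, yet has registry data on both sides of the start. Section 3.7 assumes a visit about every 3 months, and section 2.2 tabulates use of biologics and OCS at enrolment and at years 1 to 4, so treatment changes on the registry are expected.

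At stake is how far the registry can speak to its own efficacy and safety aim. Section 4.4 also plans to set its estimates beside published ones, which is hard to do if the treated group has no common starting point.

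**Working it through.** **1. The plan's own figure.** The yearly targets in section 3.2 are 2,000 + 2,000 + 1,000 + 1,000 + 1,000 = 7,000, which matches the stated target. No size is given for the newly identified subgroup or for starters of any drug, so there is no precision statement to reproduce.

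**2. What the rule selects.** For any one drug, cross time since diagnosis with time of drug start:

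| | Started before inclusion | Started on or after inclusion |
|---|---|---|
| Diagnosed within 6 months of inclusion | in | in |
| Diagnosed earlier | out | out, as written |

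The rule separates the rows. Outcome after starting a drug needs the columns separated.

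**3. Which drugs are affected.** Section 3.5 puts every entrant on step 4 or step 5 treatment, so for background controllers the top-left cell is filled by the entry rule. For biologics, entry allows prior use but does not require it. Newly diagnosed patients who start a biologic after inclusion (top-right cell) are kept.

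**4. Whether the alternative can be derived.** Start dates are listed in items 87, 90, 103 and 105. Some details need checking:
- Items 103 and 105, like 92, 94, 96, 99 and 101, are worded as start and end but show a single date response.
- Item 87 follows both the current-use question (item 85) and the earlier-use question (item 86), so it is unclear which OCS course it dates.
- The main list has age at first symptoms (item 18) but no diagnosis date. That date appears only in the screening log of section 4.8. Drug start is therefore better supported by the main list than the origin now in use.

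**5. How many starters are lost.** Two inputs are missing from the documents and are assumed here:
- f, the share of enrolled patients diagnosed within 6 months of inclusion: 5% to 50%.
- R, the chance that a newly diagnosed patient is a starter, relative to a longer-diagnosed patient: 1 to 10.

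Share of starters discarded = 1 − fR / (fR + 1 − f). For example, with f = 10% and R = 5: 1 − 0.5 / (0.5 + 0.9) = 64%.

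| f | Subgroup size, 7,000 × f | R = 1 | R = 5 | R = 10 |
|---|---|---|---|---|
| 5% | 350 | 95% | 79% | 66% |
| 10% | 700 | 90% | 64% | 47% |
| 20% | 1,400 | 80% | 44% | 29% |
| 50% | 3,500 | 50% | 17% | 9% |

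More than half are lost only when R < (1 − f)/f, that is R below 19 at f = 5%, 9 at f = 10% and 4 at f = 20%. Subgroup sizes are before restriction to any one drug.

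**The case against.** The strongest reply is that the plan is descriptive. Section 4.4 sets no hypotheses and disclaims comparison between groups. No endpoint in sections 2.1 and 2.2 is an outcome by drug; the drug items there are percentages taking or changing a therapy. The sentence at issue concerns disease outcome among treated patients, and diagnosis is a defensible origin for disease course. Longer-diagnosed patients also stay in the main tables, which cover the overall sample. All of this stands. It limits the consequence and is a reason to keep the subgroup for disease course. It does not supply a time zero for outcome on a drug, which section 4.4 nevertheless plans to analyse and section 2.0 gives as an aim.

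The second reply is that the two loosely worded clauses may widen the population. They may, so the exclusion of longer-diagnosed starters holds only for the text as written. Neither clause mentions drug start, so neither cures the problem.

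A reader might infer that most informative starters are discarded. That is plausible for a registry that enrols all attending patients, but it depends on the mix of disease durations and on starting rates, neither of which is given. At high f or R it is false.

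A reader might also infer that the subset consists of established users. Entry forces that only for background controllers, and newly diagnosed starters are retained.

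**Conclusion.** The point holds in a limited form. The subset for outcome on a drug is anchored on diagnosis and not on drug start. It necessarily includes established users of background controllers and may include established users of biologics. As written, it omits longer-diagnosed patients who start a biologic or maintenance OCS under observation. These conclusions follow from sections 3.5 and 4.4 and need no assumption.

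The size is unknown. The 9% to 95% range rests wholly on the assumed f and R and shows only that the loss could be small or large. The documents do not support a claim that the planned results are biased by a known amount or in a known direction. With no test or group comparison at risk, this is a cheap improvement.

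**What to change.** In section 4.4, replace the sentence on outcome among treated patients with text to this effect:

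> Outcome on a drug, in particular biologics and maintenance OCS, is described in patients whose recorded start date of that drug falls on or after inclusion and who have no recorded earlier use of it (for OCS, item 86), whatever the time since diagnosis. The start date is time zero. Patients already on the drug at inclusion are tabulated separately, and the counts of both groups are reported. The newly identified subgroup is used to describe disease course after diagnosis.

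Also:
- State which patients are meant by the clause joining newly identified patients with those on therapy, and what amount of data triggers the wider analysis.
- Confirm that start and end dates are stored as separate fields, and which OCS course item 87 dates.
- Say whether short courses count as earlier OCS use. Item 86 asks about any earlier use, and one route into the registry in section 3.5 is two or more systemic steroid courses in the past year.

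The cost is SAP wording and a check of the database fields. If start and end dates share one field, a small change to the eCRF may be needed. There are two downsides. Few or no new users of background ICS/LABA will exist, so little can be said about outcome after starting that class. Late starters will have short follow-up, because section 3.1 ends observation in 11.2022: a patient who starts in 11.2021 has at most 12 months.
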